#### 3.4 Study protocol

The study will be performed at the Moorfields Cataract Centre, St. Ann's outreach, London.

#### 3.4.1 Study Visits

On the day of pre-operative examination, the patient will undergo a full ophthalmic assessment and routine biometry is performed using the IOL Master by Zeiss for axial length measurement and K-readings. Additionally, a corneal topography (Pentacam) will be performed. The software for calculating the toric power is supplied by the manufacturer Rayner. The most appropriate of the available toric powers of the IOL will be used.

Surgery is performed under topical anaesthesia. Preoperatively, the horizontal meridian will be marked in the sitting position with a blue marking pen or insulin syringe at the limbus. The temporal self sealing incision, injection of viscoelastic substance, capsulorhexis, phacoemulsification, irrigation/aspiration of cortical material and injection of viscoelastic substance into the capsular bag are performed as standard procedure. According to randomisation, the multifocal toric IOL will implanted or corneal limbal relaxing incisions (LRI) according to the Donnenefeld nomogram will be performed combined with standard multifocal IOL.

The IOL is implanted via injector into the capsular bag. Following the implantation of the IOL, the toric axis is positioned in the planned axis by rotating the IOL. Then the viscoelastic

substance is aspirated thoroughly from the eye.

The LRI eye will receive a temporal or an on-axis incision with limbal relaxing incision with a 600µm single-use steel blade combined with a non-toric multifocal IOL. The location, length and site of LRIs will be made after calculation according to the Donnenfeld nomogram (www.lricalculator.com).

# Extra trial visit

3-4 months after the second eye has been operated on.

Follow-up examinations are performed as depicted in the table:

Assessments/Examinations	Visit 0	Visit 1	Visit 2	Visit 3
	PreOp	Op day (after 1 hr)	1 month	3 months
Autorefractor	х		х	х
Subjective Refraction				х
Near, Distance VA			Х	х
IOL Master Keratometry	х		Х	х
Topography (Pentacam)	х		х	Х
Retroillumination photo		х	х	х
Slitlamp examination	х	Х	Х	Х
Dysphototpsia and satisfaction questionnaire				х
Reading speed(Salzburg reading test)				х
Contrast Vision(Pelli Robson chart)				х
Glare testing(oqas)				х

Postoperative standard medication: dexamethasone gtt, qid for 2 weeks and then bid for one week, chloramphenicol gtt qid for 2 weeks

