The alternative method to reduce corneal astigmatism as part of cataract surgery is to make relaxing incisions (cuts) on the steeper axis of the cornea. This technique is in use since more than 2 decades and is widely used in clinical routine. As with toric IOLs, precise alignment of the cuts with the axis of astigmatism is essential. The disadvantage of the incisional techniques is the variability of the effect between patients since it depends on factors such as the extent of scarring of the cuts after surgery as well as corneal thickness and shape. Also, there may be a tendency for regression of the effect during the first 9 months after surgery. Furthermore there is a small risk of infection of the corneal incision and microbial keratitis after limbal relaxing incision has been described. The main advantage is the low cost.

Study objectives	Purpose of the present study is to compare the outcome of multifocal toric intraocular lens with standard multifocal lens plus incisional surgery in patients undergoing bilateral cataract surgery			
Study design	Randomised controlled trial with intra-patient comparison			
Study population	60 eyes (30 patients) with cataract and corneal astigmatism of 1.00 to 2.50 D			
Investigational Product (Medical Device)	First eye to be operated: Multifocal toric IOL (Rayner, UK), or LRI with 600µm knife according to the Donnenfeld nomogram + Multifocal IOL (Rayner, UK).			
	The contralateral eye will receive the alternative treatment			
Main outcome variables	
 
Composite scoring of unaided distance and near vision (monocularly)
 
			
	
 
Residual astigmatism evaluation by Subjective Refraction and autorefraction (Topcon)
 
			
	Any intraoperative or postoperative complications			
Additional outcome	Simulated K-readings using corneal topography (Pentacam)			

variables

Rotational stability of the IOL - angle of axis as measured from retroillumination photographs: Orientation [degrees]

- Dysphototpsia and satisfaction/ questionnaire monocularly
- Reading speed Salzburg reading test monocularly
- Glare testing monocularly(Oqas)

1		7
1.1	Background	7
1.2	Rationale	9
1.3	Risk/benefit assessment	9
2	STUDY OBJECTIVE	
3	INVESTIGATIONAL PLAN	
3.1	Design	
3.2	Selection of study population	
3	3.2.1 Number of subjects	
3	3.2.2 Pre-study screening	
3	3.2.3 Inclusion criteria	
3	3.2.4 Exclusion criteria	
3.3	Investigational Product (Medical Device)	
3	3.3.1 Medical Device (IOL) used in the study	

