The new multifocal toric lenses combine the separate optical features of a standard multifocal lens and the toric lens to provide a superior multifocal outcome with precise and sustainable toric correction.

The alternative method to reduce corneal astigmatism as part of cataract surgery is to make relaxing incisions (cuts) on the steeper axis of the cornea. This technique is in use since more than 2 decades

and is widely used in clinical routine(5). As with toric IOLs, precise alignment of the cuts with the axis of astigmatism is essential. Nomograms for these astigmatism correcting incisions are available depending on the extent and the orientation of astigmatism and the age of the patient. The disadvantage of the incisional techniques is the variability of the effect between patients since it depends on factors such as the extent of scarring of the cuts after surgery as well as corneal thickness and shape. Also, there is a tendency for regression of the effect during the first 9 months after surgery. Furthermore there is a risk of infection of the corneal incision and microbial keratitis after limbal relaxing incision has been described. The main advantage is only the low cost.

Concerning alignment, the axis is defined by either corneal keratometry or topography, or both. Misalignments may be caused intra- or postoperatively. Intraoperatively, misalignment may happen due to cyclotorsion of the eye in the lying position or due to local anaesthesia, and due to imprecision of positioning of the IOL in the bag or of placing the astigmatism correcting incisions on the cornea. These imprecisions can be dealt with by preoperative marking of the eye in the sitting position and use of meticulous positioning of the IOL or incisions during surgery.

A Rayner single-piece open-loop IOL made of hydrophilic acrylate was shown to have a good haptic memory and is thought to adhere to the capsule resulting in little to no rotation after surgery. A toric optic design has been added to this multifocal IOL design.

One of the front and back surfaces of the lens defines a toric surface for an astigmatic optical correction, and one of the front and back surfaces, which can be the same surface or the opposite surface, defines a multifocal surface for a presbyopic optical correction, to provide visual acuity for astigmatic presbyopes

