There is currently a study being conducted at Moorfields Eye Hospital comparing monofocal lenses with LRI surgery versus toric monofocal lenses. However this does not compare with the current proposal as in multifocal IOL surgery astigmatism control is definitively more important than in monofocal IOL surgery. The presence of residual postoperative astigmatism after multifocal IOLs cataract surgery is not advisable and most of the companies making multifocal IOLs advise not to operate on patients with more than 2.00 diopters of astigmatism and advocate minimizing astigmatism by means of incisional corneal surgery at the time of the cataract surgery.

Residual post-operative astigmatism leads to poor performance of multifocal lenses. One reason is that multifocal IOLs do reduce significantly contrast sensitivity especially in some light condition and adding astigmatism does have a negative impact in further reducing contrast sensitivity. Furthermore, the presence of astigmatism makes the multifocal generated near , intermediate and distance images more blurred and thus makes the brain process of learning to focus on a given image for near, intermediate and distance much more difficult for the patient.

Toric multifocal IOLs are the latest multifocal IOLS generation and do have the huge potential of massively improve the outcome of multifocal IOL surgery hence the relevance of this exploratory study. Finally whilst a monofocal toric IOL does have only a toric surface the multifocal toric IOL does have a more complex construction incorporating the multifocal and toric surfaces on one single IOL and hence comparison in terms of astigmatism reduction between the monofocal and multifocal IOLs may not be meaningful since a new variability is introduced with the multifocal toric IOL.

We plan to compare the visual performance and outcome of the non toric multifocal IOL combined with corneal incisional surgery to correct astigmatism with a toric multifocal IOL alone.

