# 1.3 Risk/benefit assessment

Safety: both IOL used are CE approved and toric monofocal is well estabilished already. One of the major problems of all studies with multifocal IOL is astigmatism correction. Hence the incorporation of toric component to the multifocal IOL should result in a better performance of the multifocal IOL in patients with corneal astigmatism.

The investigation will show whether multifocal toric IOLs are superior to corneal incisional surgery plus standard multifocal IOL that is readily used in clinical practise, in correcting astigmatism in patients with age-related cataract. This study will also show if correction of astigmatism with a toric multifocal IOL leads to better visual performance of the multifocal IOL. Since the IOL design studied is well known and has a long track record in the non-toric variant, and the non-invasive measuring procedures in this study are well tolerated, the benefit/risk ratio is acceptable. The contra lateral eye will receive limbal relaxing incisions with the multifocal IOL in the non-toric form. Since only patients that have low to moderate astigmatism are included in the trial, the difference in outcome should be small enough to not compromise binocular vision.

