# 2 Study objective

Purpose of the present study is to compare efficacy of multifocal IOL after correction of astigmatism with either implanting a multifocal toric IOL or implanting a standard multifocal IOL combined with limbal relaxing incisions.

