#### 4.6 Biometric methods

#### 4.6.1 Biometric methods - outcome variables

The outcome variables will be assessed using descriptive statistics.

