#### Components of the Visual Scoring System

The findings of this pilot study will be published by the investigators in a scientific journal and presented at scientific meetings, and will be used to power a full-scale randomised controlled trial.

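### Does a last reading at 3-4 months undermine the comparison, given that the protocol expects the LRI effect to regress over 9 months?

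*Protocol*

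**What the plan says.** Two places in the protocol describe how incisional correction behaves over time. The synopsis background is hedged: "there may be a tendency for regression of the effect during the first 9 months after surgery". Section 1.1 states it as fact: "there is a tendency for regression of the effect during the first 9 months after surgery". Neither gives an amount in dioptres or the shape of the decline.

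Section 3.4.1 (Extra trial visit) sets the last assessment at "3-4 months after the second eye has been operated on". The visit table in the same section heads its last column 3 months and shows nothing later. Section 3.2.4 asks for the second eye to be listed within 3-4 weeks where possible, so the gap between the operations is a target and not a fixed limit.

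On what the study is for, section 1.1 ends its argument with "hence the relevance of this exploratory study". Section 2 gives the purpose as to "compare efficacy of multifocal IOL after correction of astigmatism". Section 4.6.1 says: "The outcome variables will be assessed using descriptive statistics". Section 1.3 goes further in tone: "The investigation will show whether multifocal toric IOLs are superior to corneal incisional surgery plus standard multifocal IOL". The closing part of section 4.7 says that the findings "will be used to power a full-scale randomised controlled trial". None of these statements names a time point.

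**The concern.** Residual astigmatism is a main outcome, and it is the outcome most directly exposed to loss of the LRI effect. If the effect fades over 9 months and the last reading comes at 3-4 months, the LRI eye is measured before the decline has run its course, while the toric eye is not expected to decline in that way. On the protocol's own premise the contrast is then tilted on average towards LRI.

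Two consequences would follow. A null or small difference could be taken as lasting equivalence, although it describes only the early months. And if the observed difference were carried into the sample size of a later trial with a later endpoint, that trial could be the wrong size. A reader who goes from the regression statement in section 1.1 to the superiority wording in section 1.3 could fairly ask why no time limit connects them.

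**Working it through.** **Is there a figure to reproduce?** No. The protocol gives 30 patients (60 eyes) without a calculation, and states no significance level, power, effect size or standard deviation. The check is calendar arithmetic and a reading of the passages against each other.

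**Inputs.** Last visit 3 to 4 months after second-eye surgery (section 3.4.1); gap between eyes up to 4 weeks as a target (section 3.2.4); regression period 9 months (synopsis and section 1.1).

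**Age of the LRI eye at the last reading.**
- LRI in the second eye: 3 to 4 months.
- LRI in the first eye, 4-week gap, latest visit: 4 + 28/30.4 = 4.92 months.

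**Part of the 9 months not observed.**
- Earliest reading: 9 - 3 = 6 months, 6/9 = 67%.
- Second eye, latest visit: 9 - 4 = 5 months, 5/9 = 56%.
- First eye, latest visit: 9 - 4.92 = 4.08 months, 4.08/9 = 45%.

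The last reading therefore lies inside the stated regression period for either order of surgery. An LRI-first eye would reach 9 months only if the operations were 9 - 4 = 5 to 9 - 3 = 6 months apart. The 45% is not a firm lower bound, because the 4-week gap is only a target.

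**Direction.** If LRI eyes on average lose correction after the last visit, the LRI result at 3-4 months is better than it will be later. A toric advantage seen at that visit would then be understated. The opposite could occur only if, for example, many LRI eyes were overcorrected and drifted towards zero cylinder.

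**Effect on powering.** Let k be the later difference divided by the pilot difference, with the same standard deviation. Required size is proportional to 1/k², so a later-endpoint trial sized on the pilot difference has k² times the size it needs:
- k = 1.25: 1.25² = 1.56 times the need.
- k = 1.5: 1.5² = 2.25 times the need.
- k = 0.75: 0.75² = 0.56 of the need.

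Every k here is an assumption. The values lie on both sides of 1, so even the direction of mis-sizing cannot be fixed from the protocol. The calculation also presupposes two things that section 4.7 does not say: that the pilot mean difference, and not only its variability, will be the planning value, and that the later trial will have a later endpoint. With a 3-4 month endpoint, the mismatch disappears.

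**Wording against schedule.** Section 1.3 asks whether the toric lens is superior. It announces no answer and says nothing about how long an advantage would last. The objective in section 2 is a neutral comparison. No superiority test is specified that the timing could invalidate.

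**The case for a change.** The best case for a change is that it would be almost free. Section 1.3 is the plainest statement of what the study will answer, and it is unqualified. The protocol elsewhere presents durability as part of the appeal of the toric lens, which the schedule cannot test over the 9 months it names. Feeding a later trial is a declared use of these data, so the time point to which the estimate belongs matters. A statistical analysis plan would not normally rewrite a risk/benefit section, so the limit would have to be placed in the protocol. Two short qualifications would do it. A descriptive table of change between the 1-month and 3-month visits could be added from autorefraction and corneal readings already scheduled.

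The facts in this argument stand: the last reading is inside the regression period, and neither statement carries a date. What does not follow is a defect. The regression is disclosed openly in the same document as the visit schedule, and any competent report will present its results as results at 3-4 months. The table would not meet the point either. It would cover at most 4.92 - 1 = 3.92 months of change and nothing after the last visit, which is where the unobserved regression lies. It is also ordinary descriptive content that analysts can add without a protocol change.

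**Conclusion.** No change follows. The timing observation is correct: about 4.1 to 6 of the 9 months lie beyond the last reading, taking the listed gap between eyes as met. But for an exploratory pilot of 30 patients with descriptive analysis, a 3-4 month follow-up is a fair trade-off. Carried out as written, it yields a valid within-patient description at that time. The expected tilt is, on average, against the toric lens, so it would not create a spurious advantage for it.

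What remains is a possible misreading of a null result as lasting, and a possible misuse of the difference in planning a trial whose endpoint is not given. Neither can be sized from the protocol, since it states no amount of regression, no standard deviation and no planning effect. Someone editing section 1.3 for other reasons could add that the comparison is at 3-4 months and does not capture later LRI regression. That would be a courtesy to the reader and would change no estimate, table or conclusion.

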#### 3.4.2 Withdrawal and replacement of subjects

Subjects must be withdrawn under the following circumstances:

- at their own request

#### 3.5 Variables and schedule of observations

#### 3.5.1 Outcome variables

Main outcome variables	•	
 
Composite scoring of unaided distance and near vision (monocularly and binocularly)
 
		
	•	Residual astigmatism evaluation by Subjective Refraction and autorefraction (Topcon) and		
	•	Any intraoperative or postoperative complications		

Additional outcome	Simulated K-readings using corneal topography (Pentacam)			
variables	Rotational stability of the IOL - angle of axis as measured from retroillumination photographs: Orientation [degrees]			
	
 
Dysphototpsia and satisfaction questionnaire - monocularly
 
			

- Reading speed Salzburg reading test monocularly
- Glare testing (Oqas)– monocularly
- Post-operative dominance will be established using the visual acuity results to ensure that there are equal numbers of dominant and non-dominant eyes in both groups

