# 3.2.1 Number of subjects

60 eyes of 30 patients with bilateral cataract.

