# 3.2.4 Exclusion criteria

Any of the following will exclude a subject from the study:

Relevant other ophthalmic diseases such as: pseudoexfoliation, glaucoma, traumatic cataract corneal scars, and other co-morbidity that could affect capsule bag stability (e.g. Marfan syndrome)

- Irregular corneal astigmatism on Pentacam topography
   Surgery should be :
- Performed by consultants
- Second eye to be listed within 3-4 weeks whenever possible.

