# 4.3 Assessment of visual acuity

Measurement of uncorrected and best corrected visual acuity will be done using a back-lit EDTRS chart placed at 4m.

Near and distance unaided and corrected visual acuity will be measured

Reading speed, reading acuity and ciritical print size monocularly (Salzburg Reading Desk)

The Salzburg Reading Desk (SRD) is the prototype of a reading chart that measures reading speed and reading distance. Contrast and light conditions are preset and reading distance (+/- 0.2 cm), reading speed and their changes during the examination are measured. This ensures an objective evaluation of measurements under the same conditions at every follow-up.

Contrast vision under photopic and mesopic conditions (Pelli-Robson Chart)

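### Does it matter that section 3.5.1 scores the visual composite with one eye and with both, while the synopsis scores it with one eye only?

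*Protocol*

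**What the plan says.** The synopsis lists the first main outcome as "Composite scoring of unaided distance and near vision (monocularly", with nothing after that word inside the bracket. Section 3.5.1 lists the same outcome as "Composite scoring of unaided distance and near vision (monocularly and binocularly".

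The places that might settle the matter do not. The visit table has a row "Near, Distance VA", marked at 1 month and 3 months, with no mention of one eye or both. Section 4.3 states "Near and distance unaided and corrected visual acuity will be measured", again without saying which.

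The design is a comparison within patients. The synopsis says of the fellow eye: "The contralateral eye will receive the alternative treatment". Section 3.2.1 sets the size at "60 eyes of 30 patients with bilateral cataract". The additional trial visit takes place "3-4 months after the second eye has been operated on".

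Section 4.6.1 limits the analysis of outcomes to descriptive statistics. Section 4.7 proposes a four-category composite and leaves its construction to be decided from the pilot data together with the questionnaire.

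**The concern.** A main outcome should have one definition, and here the two lists differ on whether a binocular score belongs to it. Elsewhere the Protocol does state laterality: section 3.5.1 marks reading speed, glare testing and the questionnaire as monocular. Its silence on acuity in the visit table and in section 4.3 therefore leaves a gap.

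The two scores also differ in kind. The monocular score belongs to an eye, and so to a treatment. Once both eyes have been operated on, the binocular score belongs to a patient who carries both treatments. It cannot address the objective in section 2, which is toric multifocal lens against standard multifocal lens plus LRI. Section 3.5.1 nevertheless puts both scores on one line and gives the binocular one no stated purpose.

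If a reader took the binocular score as evidence on the treatments, or if it displaced the monocular score, the main comparison would be muddied. The pilot is also meant to inform the size of a later trial, so it should be clear which score is carried forward.

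**Working it through.** The Protocol gives no power or sample-size calculation to reproduce, so the check is a comparison of the two wordings and a count of what each yields.

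**Inputs**
- Patients: 30; eyes: 60 (section 3.2.1).
- Allocation: one eye toric, fellow eye LRI with the non-toric lens (synopsis; section 3.1 for the within-patient design).
- Analysis: descriptive (section 4.6.1).
- Assumption: complete data at the time point considered.

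**Monocular composite, per time point**
- Scores: 30 × 2 = 60.
- By treatment: 30 toric and 30 LRI.
- Within-patient differences: 30.

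**Binocular composite, per visit after both operations**
- Scores: 30 × 1 = 30 at most, all from patients with one toric and one LRI eye.

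| | Synopsis wording | Section 3.5.1 wording |
|---|---|---|
| Toric monocular scores | 30 | 30 |
| LRI monocular scores | 30 | 30 |
| Within-patient differences | 30 | 30 |
| Binocular scores (one per patient) | 0 | up to 30 |

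Only the last row differs, and that row holds no treatment comparison under either wording.

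**Is a misuse of the binocular score planned?** No section says it will be compared by treatment. With one treatment per eye there is no group of patients to compare it between, so an analyst could not tabulate it by arm by mistake. The only available summary is a single distribution over patients.

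**Is there a sensible reading of it?** Yes. The introduction's aim of spectacle independence concerns the patient, not one eye. Section 1.3 expects that treating the two eyes differently will not compromise binocular vision. The Protocol does not link the score to either point, but both make a per-patient summary reasonable.

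**Is the later trial affected?** The variability that a later paired-eye trial would need comes from the 30 within-patient monocular differences, which are the same under both wordings.

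**The case for a change.** The strongest case for a change is that both lines are current text and both phrases are complete, so the conflict is not an artefact of how the document was read. What a main outcome measures is a matter for the protocol, and an analysis plan would have to choose between the two. Staff cannot tell from the visit table or section 4.3 whether a binocular test is required, and a test left out cannot be recovered afterwards.

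The inconsistency stands, and so does the point about unrecoverable data. What could be lost, however, is a descriptive per-patient summary, not any part of the toric-versus-LRI comparison. The study runs at one centre (section 3.4) with a case record form for each patient (section 4.5). Whichever reading is adopted can therefore be applied uniformly, although the form itself is not shown.

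The missing statement of purpose carries little weight, since the Protocol gives no separate purpose for any individual outcome.

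A timing argument could be added. Acuity is scheduled at 1 month, while section 3.2.4 says only "Second eye to be listed within 3-4 weeks whenever possible", so a binocular score might combine a treated eye with an unoperated one. That requires the visit to be counted from first-eye surgery, the second eye to be delayed beyond that visit, and a binocular composite to be taken then. The Protocol states none of these, so the argument does not hold.

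**Conclusion.** The synopsis and section 3.5.1 do disagree, on one of three main outcomes, about whether the visual composite is also scored binocularly. This is a clerical inconsistency. Following either wording, the sponsor obtains the same 60 monocular scores and the same 30 within-patient differences per time point, summarised descriptively in a pilot whose composite is still provisional. The effect on the treatment comparison is nil. The effect on the report is at most the presence or absence of up to 30 per-patient binocular scores at a visit, which an analyst would naturally present as a single descriptive distribution. Tidying the wording would do no harm, but it would alter no result or conclusion, so no change is called for.

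This rests on three conditions: acuity is measured in each eye separately, as both lists require; the binocular score is not used to judge one treatment against the other, which the Protocol nowhere proposes; and the analysis stays descriptive, as section 4.6.1 states.
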